#### 7.2. Discussion of Study Design, including the Choice of Control Groups

This trial is designed as a phase 2b, randomized, double blind, parallel group, placebo controlled, multicentre, 6-week dose-finding study to assess the efficacy and safety of Bavisant for the treatment of excessive daytime sleepiness in subjects with Parkinson's disease.

There is no regulatory approved pharmacological agent for the treatment of excessive daytime sleepiness and despite the use of agents such as modafinil (Provigil), which have not shown consistent and reliable effectiveness, there is still a real unmet need in the subject population. Bavisant has a unique mechanism of action and may be able to address this need.

The intention of the proposed selection criteria is to limit participation to PD subjects with moderate sleepiness and ability to complete the study assessments without any major impairment that may impact the collection of either the efficacy endpoints (should have moderate sleepiness due to PD only and no other conditions, be on stable medication without interference of concomitant medication as assessed before study participation, have no clinical evidence of suicidal ideation, depression, cognitive impairment, or fatigue) or the safety endpoints (hepatic, renal, cardiac, ophthalmological). The inclusion criteria of the planned clinical study are intended to select adult subjects (50-80 years old, both inclusive), with a previous diagnosis of Parkinson's disease (PD), and an objective assessment of at least moderate excessive daytime sleepiness

Protocol No.: BB-2001-201b EudraCT No.: 2017-000877-35 Amendment 04, Final Version 1.0 07/Nov/2018 Page 40 / 142

(EDS) (Epworth Sleepiness Score [ESS] > 12 at screening). Stable medication for at least 4 weeks before screening is mandatory regarding medication which may affect sleep (for example, dopaminergics, L-dopa, monoamine oxidase inhibitors, antipsychotics, or hypnotics). The exclusion criteria will exclude subjects with EDS due to conditions other than Parkinson's disease (including narcolepsy and sleep apnoea), any significant eye disease which may have an impact on a subject's mobility (which could hamper the study assessments), clinical evidence of depression (HAM-D score ≥ 17, as a certain degree of depression is shown by most of the PD subjects), positive response on the C-SSRS (an answer of 'yes' to any of the 6 questions), clinical evidence of cognitive impairment (MoCA score  $\leq 22$ , as it could interfere with the study assessments), clinical evidence of fatigue (FSS  $\geq$  36, for similar reasons), any alerting medication (including r-modafinil, modafinil or methylphenidate), benzodiazepines, histamine active agents, clozapine, atomoxetine, skeletal muscle relaxants, or any other daytime medications which affect sleep (in order to avoid any selection bias). Subjects with hepatic, renal, cardiac (ECG, including QTc), or ophthalmological impairment will not be entered into the study. The suicide risk will be assessed (C-SSRS) before and after treatment administration at all study visits including followup following the the FDA Guidance for Industry on Suicidal Ideation and Behavior. BPRS+ (Brief Psychiatric Rating Scale) positive subscale to monitor psychotic symptoms and HAM-D to monitor depression will be assessed at all study visits (including follow-up). These assessments are included because patients with Parkinson's disease are known to be at higher risk of psychosis and depression than the general population. Follow-up procedures for a positive finding on the C-SSRS, or an elevated HAM-D or psychosis scale score will be managed as per the standard of care at the site, including an assessment by the investigator of the need for further mental health evaluation. Vital signs (including blood pressure and heart rate) will be assessed at all study visits (including follow-up) as patients with Parkinson's disease are known to commonly exhibit orthostatis and other cardiovascular changes.

The Bavisant doses for this study have been selected based on data from previous preclinical and clinical research and are lower than the previously anticipated maximum clinical dose of 10 mg/d (for more details, please refer to the Investigator Brochure Ed. 9, 2017). Bavisant has been evaluated at dosages of 10 mg/d or lower in a total of 9 clinical trials and 481 subjects: 4 phase 1 studies in healthy adult subjects, 1 study in healthy elderly subjects, a phase 1 study in Japanese healthy adult male subjects, 2 phase 1 studies in children with ADHD, and a phase 2b study in adult subjects with ADHD. Bavisant has also been used at dosages higher than 10 mg/d in 5 clinical trials and 198 subjects: 4 phase 1 studies in healthy adult subjects and a phase 2a study in men with ADHD. No relevant safety issues are expected since the most common treatment emergent adverse events reported (at least 5%) in the Bavisant 10 mg/d group compared to placebo were: middle insomnia (27.4% vs 0%), initial insomnia (24.7% vs 6.8%), nausea (19.2% vs 1.4%), abnormal dreams (17.8% vs 0%), insomnia (15.1% vs 4.1%), dizziness (12.3% vs 0%), and dysgeusia (12.3% vs 0%). Levels of these events at 1 and 3 mg were lower than at 10mg/d.

The Epworth Sleepiness Scale (ESS) has been selected for the evaluation of the study primary endpoint because this is a well-established validated tool for assessing EDS. Normal range is between 0 and 10 (2.5 and 97.5 percentiles) which corresponds to "lower normal" (0-5) and "higher normal" (6-10). Other ranges can be interpreted as "mild excessive" (11-12), "moderate excessive" (13-15) and "severe excessive" (16-24); so in order to control the variability of the

Protocol No.: BB-2001-201b EudraCT No.: 2017-000877-35 Amendment 04, Final Version 1.0 07/Nov/2018 Page 41 / 142

ESS, the current study requests the categories of either "moderate excessive" or "severe excessive" ESS for the study (>12). As the ESS questionnaire is not suitable for use among people with serious cognitive impairment, correspondingly subjects with evidence of significant cognitive impairment will be excluded from the study (MoCA score  $\leq 22$ ).

The ESS, together with the Multiple Sleep Latency Test (MSLT) and the Maintenance of Wakefulness Test (MWT), are three of the most widely used tests of daytime sleepiness. Although all these three tests give results that are significantly correlated statistically, the ESS has been selected as the primary endpoint for the study as it is considered to be the most discriminating test of average of sleep propensity and sleepiness in daily life than either the MSLT or the MWT. The observation of the US modafinil study group on the effects of modafinil in reducing the EDS of narcoleptics was shown more clearly in ESS than the MWT, and least by the MSLT. The ESS, which is based on retrospective subjective reports, has been shown to produce more accurate results than the objective measurement made of the mean sleep latency (SL) in the MSLT or MWT. One reason is that the MSLT and MWT can each measure only one situational sleep propensity, each of which is correlated in an uncertain way with what is intended to be measured the average of many different situational sleep propensities that reflect the activities of daily life. The ESS provides an estimate of the latter, the average sleep propensity in eight specified situations. Whatever cut-off point is used with the mean MSLT-SL it will tend either to misdiagnose a significant number of normal subjects as having EDS (false positives) or will fail to diagnose some narcoleptics or subjects with other sleep disorders as having EDS (false negatives). To do a MSLT or MWT on all subjects suspected of having EDS is difficult to justify when the ESS is a more discriminating test, is far cheaper and easier to administer with less burden on the patient. On the other hand, the ESS has a clear external validity, and this is the reason why the ESS has been already used to confirm the treatment effect (modafinil) on excessive daytime sleepiness (although not in Parkinson's disease).

The polysomnography and MWT will be performed locally by sites that have the practice parameters to develop the MWT assessment in accordance with the recommendations developed by the Standards of Practice Committee and reviewed and approved by the Board of Directors of the American Academy of Sleep Medicine . This is key to standardise the procedure at all participating sites.

The study sample size is based on the expected Epworth Sleepiness score (ESS) change from baseline after 6 weeks of treatment. The endpoint of 6 weeks has been selected as this is a valid time frame for the ESS scale ('Respondents to the ESS rate their chances of having dozed off or fallen asleep in particular situations in "recent times". [...] intended to mean a few weeks to a few months, not a few hours or days.', Johns, http://epworthsleepinessscale.com/about-the-ess/). We consider the effect of Bavisant in sleepiness can be observed within 6 weeks which is a valid recall period for the ESS, and also there are results already published from clinical trials after even lower periods (2 weeks with modafinil in a crossover design in another indication, 3 weeks with caffeine [ClinicalTrials.gov NCT00459420]). The parallel design is preferred over a crossover design which can always present a carryover effect which could bias the second period.

Although there is not any published agreement on the minimal clinically important difference (MCID) for the ESS, the distribution-based method of the standard error of measurement has been

Protocol No.: BB-2001-201b EudraCT No.: 2017-000877-35 Amendment 04, Final Version 1.0 07/Nov/2018 Page 42 / 142

previously used, and that is the method chosen for this study. As there is no previous reported experience in parallel designs of the standard error of the ESS in Parkinson's disease, the assessment report of pitolisant has been used as a reference (EMA/828546/2015). The sample size of the corresponding studies, although in another indication, was calculated under the hypothesis derived from historical trials with a MCID of 3.0 and a standard deviation of 5.0. This study will give the assumptions for further research which may use the distribution-based method of the standard error once there is experience with Bavisant used in EDS in PD.

As there is no previous data published on ESS which demonstrate a positive effect of ESS in excessive daytime sleepiness in Parkinson's disease, the assumptions used for the sample size calculation are based on the pitolisant EPAR with (a) a mean absolute change in the Epworth Sleepiness Scale (ESS) from baseline to the end of 6-week treatment period of at least 3.0 points and (b) a standard deviation of 5.0 which showed an ESS decrease between 2.5 and 2.7 at baseline.

The effect size of Bavisant in EDS is unknown. Smaller changes in ESS may be detected that may be clinically useful. In addition, although higher variability is expected in this multicentre study, variability may be lower as the selection criteria restricts a baseline ESS > 12.0 points (compared to 10.0 by other studies). Therefore, in order to confirm both the intragroup statistical decrease in daytime sleepiness together with the intergroup statistical comparison vs. placebo, a total sample size of 200 completed subjects (50 per treatment group + expected 15% of early withdrawal rate) is proposed in this planned first study. The study will be powered to detect a minimum 3.0 point difference in the ESS change from baseline compared to placebo assuming an SD range from 4.0 to 5.3 ( $\alpha$ =0.05;  $\beta$ =0.20; power=80%;  $\Delta$ =3.0; SD=5.0).

Finally, a placebo control group has been considered relevant for the study among other reasons because the primary endpoint is a self-reported assessment, subjective by nature. This subjectivity is controlled by intra-subject comparisons compared to baseline score, and by statistical methods (ANCOVA and MMRM models); but an additional control group with placebo could be considered as the natural progression of the EDS within a clinical trial environment. In any case, the subjects will be informed about the possibility of receiving placebo, the possible consequences and their right to withdraw from the study at any time.

Amendment 04, Final Version 1.0
Protocol No.: BB-2001-201b
EudraCT No.: 2017-000877-35
Page 43 / 142

# 8.0 Selection of study Population

The subject population will comprise male and female subjects of any race, aged between 50 and 80 years at Day 1, with a previous diagnosis of Parkinson's disease and a medical history of excessive daytime sleepiness confirmed with an Epworth Sleepiness Scale (ESS) > 12 at screening which correlates to at least moderate sleepiness ("moderate excessive" [13-15] and "severe excessive" [16-24]). Prior to any and all study-specific examinations, subjects will be informed as to the extent and nature of their study participation and will be given the opportunity to provide their written informed consent.

Approximately 48 active study sites globally will randomize a total of 230 subjects in order to have at least 200 completed subjects (50 completed subjects per treatment group, assuming an early withdrawal rate of around 15%). Recruitment will be competitive throughout all counties and sites.

Both inclusion and exclusion criteria will be assessed during the screening period and reconfirmed during the baseline period (see Section 8.1 and Section 8.2, respectively). Corresponding information should be provided in the eCRF.

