### 7.0 Investigational Plan

# 7.1. Overall Study Design and Plan: Description

This phase 2b study is designed as multicentre, multinational, randomized, double blind, parallel group and placebo controlled with three doses of Bavisant (0.5, 1, and 3 mg/d) in subjects with excessive daytime sleepiness with Parkinson's disease. This study will involve approximately 230 subjects from around 48 sites globally.

Eligible subjects will be randomly allocated at a ratio of 1:1:1:1 to either Bavisant (at doses of 0.5, 1, and 3 mg/d) or placebo.

After signing the study informed consent, subjects meeting the UK PDS Brain Banks Diagnostic Criteria for Parkinson's disease (see details in Appendix 18.2) will enter a screening period (lasting up to 3 weeks) followed by a baseline period (lasting up to 1 week). Key inclusion / exclusion criteria will be verified to determine subject eligibility at the screening, baseline periods and prior to randomisation, including the suicide risk assessment following the FDA Guidance for Industry on Suicidal Ideation and Behavior.

[figure not shown]
There is a 6 weeks treatment period, starting on Day 1, followed by a safety follow-up at least 4 weeks after completion of the treatment period. Additional unscheduled visits may be required based on the investigators' judgement at the end of study visit or at the safety follow-up. For early termination, all the assessments of the treatment week 6 visit should be performed, if possible, including the safety follow-up 4 weeks after the last IMP administration.

A schematic of the study design is included in Figure 1 and the schedule of assessments is listed in Appendix 18.15.

Protocol No.: BB-2001-201b 07/Nov/2018 EudraCT No.: 2017-000877-35 Page 39 / 142

Figure 1. Study figure

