# 8.5.2 Discontinuation or Withdrawal of Individual Subjects

If a randomized subject terminates the study prematurely for any reason, all attempts should be made by the investigator to perform the procedures for the early termination visit (same as for the week 6 visit) and determine the primary reason for the termination and where possible the primary underlining reason, providing as much as detail as possible, and documenting the information on the eCRF. Randomized subjects will not be replaced.

The primary reason for discontinuation or withdrawal of the subject from the study should be noted using the following categories:

- (1) Pretreatment event (PTE) or Adverse Event (AE). The subject has experienced an adverse event or pre-treatment event that requires early termination because continued participation imposes an unacceptable risk to the subject's health or the subject is unwilling to continue because of the adverse event or pre-treatment event.
- (2) Noncompliance with investigational medicinal product (IMP). This includes subjects who did not take the study drug for more than 6 consecutive days.
- (3) Major protocol deviation. The subject failed to meet protocol entry criteria or did not adhere to protocol requirements, and continued participation poses an unacceptable risk to the subject's health, or a major protocol deviation occurred at the site such as the blind was broken.
- (4) Withdrawal of consent. The subject (or subject's legally acceptable representative) wishes to withdraw from the study. The reason for withdrawal, if provided, should be recorded in the case report form (eCRF). Subjects may withdraw from the study at any

Amendment 04, Final Version 1.0
Protocol No.: BB-2001-201b
EudraCT No.: 2017-000877-35
Amendment 04, Final Version 1.0
07/Nov/2018
Page 65 / 142

time at their own request without giving reasons and without any disadvantageous consequences for their subsequent medical care.

- (5) Lost to follow-up. The subject did not return to the clinic and attempts to contact the subject were unsuccessful. Attempts to contact the subject must be documented.
- (6) Subject does not fulfil randomisation criteria.
- (7) Other.

In the case of study termination by the sponsor, institutional review board (IRB), independent ethics committee (IEC), or regulatory agency, reason for withdrawal should be captured as Other, Study Termination.

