#### 11.0 Statistical Methods and Determination of Sample Size

#### 11.1. Statistical and analytical plans

The statistical analysis will be performed by the Department of Biostatistics of Linical, using SAS® version 9.2 or later.

Statistical significance will be assessed for two-sided probability values < 0.05.

All descriptive variables will be tabulated. Quantitative variables will be described showing their number of available and missing observations, mean, median, standard deviation (SD), the range (minimum and maximum) and the first and third quartiles. Frequency and percentage will describe qualitative variables. Missing values will be tabulated with their frequency but will not be included in the calculation of percentages.

The main population for the efficacy analysis will be the intent to treat population (ITT). The per protocol population (PP) will be analysed also as a sensitivity analysis.

The main population for the safety analysis will be the safety population (SAF), defined as all the subjects who have received at least one dose of study treatment.

Full details of the statistical analysis will be given in a Statistical Analysis Plan (SAP) which will be prepared, approved and signed before the database closure, and so before the subjects' evaluability assessment.

Any deviation from the original SAP will be included and reported in the clinical study report (CSR).

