#### 11.2. Determination of sample size

A total of 200 completed subjects will be evaluated for the study (50 completed subjects per treatment group, with expected early withdrawal rate of around 15%).

The assumptions used for the sample size calculation are a mean absolute change in the Epworth Sleepiness Scale (ESS) from baseline to the end of the 6-week treatment period of at least 3.0 points (minimum change considered as clinically relevant) and a standard deviation of 5.0 (based on a comparable study of Modafinil in a similar population recruited at one centre which showed a standard deviation in the ESS between 3.5 at baseline and 4.8 at the end of the treatment period) and a reduction in ESS of 2.7 points for subjects treated with Modafinil.

The confirmation of the hypothesis of detecting a mean difference in ESS of 3.0 points vs. baseline requires a sample size of 25 subjects per group (intragroup  $\Delta$ =3.0; SD=5.0; two-side  $\alpha$ =0.05;  $\beta$ =0.20; power=80%; one-sample t-test).

The additional endpoint of showing a statistically significant difference of at least 3.0 points in ESS between Bavisant and. placebo requires a sample size of 50 subjects per group (between treatment  $\Delta$ =3.0; SD=5.0; two-side  $\alpha$ =0.05;  $\beta$ =0.20; power=80%; two-sample equal-variance t-test).

Amendment 04, Final Version 1.0 07/Nov/2018 Page 82 / 142

The effect size of Bavisant in EDS is unknown and smaller changes in ESS may be clinically useful according to its profile, and higher variability is expected in this multicentre study; so the sample size of 200 completed subjects (50 per treatment group) is proposed in order to cover both the confirmation of an intragroup change of at least 3.0 points vs. baseline, and the between-group difference of at least 3.0 points change vs. placebo.

The Maintenance of Wakefulness Test (MWT) will be performed in a minimum of 20 subjects per group (80 overall) in order to be enough to show statistically significant differences if the expected MWT absolute change from baseline differs at least in one standard deviation (effect size = 1.0).

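### At the protocol's own 15% withdrawal rate, randomising 230 gives about 196 completers (49 per arm), not at least 200 (50 per arm)

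*Protocol*

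**What the plan says.** Section 8.0 of the protocol is the one place where all the figures meet. The sites "will randomize a total of 230 subjects in order to have at least 200 completed subjects", and the bracket that follows explains this as "50 completed subjects per treatment group, assuming an early withdrawal rate of around 15" per cent.

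The same components recur separately:

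- Protocol 7.1: "This study will involve approximately 230 subjects from around 48 sites globally". Section 4 of the SAP repeats this number. Allocation is equal: "Eligible subjects will be randomly allocated at a ratio of 1:1:1:1".
- Protocol 7.2 words the allowance as an addition: "50 per treatment group + expected 15% of early withdrawal rate".
- Protocol 11.2, repeated in SAP section 5, gives "50 completed subjects per treatment group, with expected early withdrawal rate of around 15" per cent. It states that the comparison with placebo requires 50 per group (difference 3.0, SD 5.0, two-sided alpha 0.05, power 80%, two-sample t-test).
- The protocol summary gives 200 completed subjects in the population block and approximately 200 in the sample-size paragraph.
- Protocol 8.6.6 says that randomisation aims at 200 completers.
- Protocol 8.5.2: "Randomized subjects will not be replaced".

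**The concern.** Section 8.0 states a minimum number of completers, a number to randomise and a withdrawal rate, and the three cannot all hold. If 15% of 230 subjects withdraw, fewer than 200 complete. Because withdrawn subjects are not replaced, nothing in the plan makes up the difference.

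What is at stake is the accuracy of a stated design figure. Fifty completers per arm is the number that section 11.2 says the placebo comparison requires, and section 7.2 claims power over an SD range up to 5.3. A reader who sets the final completer count against the protocol would be using a target that the protocol's own inputs are not expected to meet.

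**Working it through.** **Inputs.** 230 randomised, at least 200 completers, 50 per arm and 15% withdrawal (protocol 8.0). Four equal arms (7.1). Difference 3.0, SD 5.0, two-sided alpha 0.05, two-sample t-test (11.2). SD range 4.0 to 5.3 (7.2).

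**1. Reproducing the plan's figure.** 200 × 1.15 = 230, an exact match. It also fits the additive wording in section 7.2.

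**2. Completers expected from 230.** 230 × (1 − 0.15) = 195.5. Per arm: 195.5 / 4 = 48.9. The shortfall against 200 is 4.5 subjects.

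**3. Number needed for 200 at 15%.** 200 / (1 − 0.15) = 235.3, rounded up to 236, or 59 per arm. Check: 236 × 0.85 = 200.6. The gap is 236 − 230 = 6 randomised subjects.

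**4. Withdrawal rate at which 230 is enough.** 1 − 200/230 = 13.0%. At 14%, 230 × 0.86 = 197.8, still short.

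**5. Chance of meeting the stated minimum.** If each subject withdraws independently with probability 0.15 (an assumption made here), completers follow a binomial distribution. The probability of at least 200 is 23% with 230 randomised and 59% with 236.

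**6. Effect on power.** Two-sample t-test, difference 3.0, two-sided alpha 0.05:

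| Completers per arm | SD 5.0 | SD 5.3 |
|---|---|---|
| 50 | 84.4% | 80.0% |
| 49 | 83.6% | 79.2% |
| 45 | 80.4% | 75.7% |

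At SD 5.0 the smallest whole number per arm that reaches 80% is 45 (exact solution 44.6), so the plan's 50 already carries a margin. At SD 5.3 there is no margin: 50 per arm gives 80.0%, and one completer fewer per arm falls just below.

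**The case against.** The figures are hedged. Withdrawal is around 15%, section 7.1 makes 230 approximate, and the sample-size paragraph of the summary makes 200 approximate. A rate of 13% might pass as around 15%, and six subjects are only 2.6% of 230. This is fair as to size. It does not rescue section 8.0, which states a total of 230 and a minimum of 200 without hedging either, and misses that minimum at its own central rate.

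Section 8.6.6 ties randomisation to 200 completers, so one could read 230 as a forecast with no cap. The bar on replacement does not itself set a cap either. But section 8.6.6 gives no rule for continuing past 230, and section 8.0 names 230 as the total.

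Completers are not the sample for the primary analysis in the SAP. SAP sections 6, 9.1 and 10.1 describe an ANCOVA on all randomised and dosed subjects, with missing post-baseline ESS multiply imputed. An early-termination ESS taken within the window in SAP section 4.1 can also stand in for week 6. This stands, so the power figures above check the plan's own completer calculation only. It does not remove the inconsistency, because both documents size the trial on completers.

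A reader might infer that the trial is underpowered. The documents do not support that: at SD 5.0, the value in the calculation, power stays above 80% down to 45 completers per arm. With 230 randomised, that allows withdrawal of about 22% (1 − 180/230 = 21.7%). A reader might also take the multiplication by 1.15 as established. It is well supported by the exact match and by the wording of section 7.2, but no formula is shown.

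**Conclusion.** The inconsistency is real and small. On the protocol's own central assumption, 230 randomised subjects yield 195.5 completers, about 49 per arm, which is 4.5 short of the stated minimum. The stated minimum holds only if withdrawal is 13.0% or less.

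The loss of power is under one percentage point. Power falls below the stated 80% only at SD 5.3, and then by less than a point. The conclusion takes 15% at face value and assumes equal withdrawal across arms and no randomisation beyond 230. The power figures are for a t-test on completers and should not be read as the power of the SAP's imputed ANCOVA. This is a correction of a stated figure. It gives no ground for redesigning the trial.

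**What to change.** In protocol section 8.0, state 230 randomised and about 196 completers (about 49 per arm) at 15% withdrawal. Bring the statements of 200 or 50 completers into line in the protocol summary, protocol 7.2, 8.6.6 and 11.2, and SAP section 5. Protocol 7.1 and SAP section 4 give only the number 230 and can stay as they are. Where power is quoted, 49 per arm gives 83.6% at SD 5.0 and 79.2% at SD 5.3. The claim in section 7.2 that 80% power covers SDs up to 5.3 should be worded to match.

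The withdrawal rate should not be changed to 13% to make the figures agree. The documents offer no basis for 13%, and choosing it would fit the assumption to the enrolment number. If the sponsor prefers to keep 200 as the expected number of completers, the matching number to randomise is 236.

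Restating the completer figure costs wording only, and the stated figure becomes slightly less favourable. Keeping 200 costs six more randomised subjects.
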